5.3 Lifestyle Considerations

5.3.1 Meals and Dietary Restrictions

Subjects must fast at least 8 hours prior to the collection of specimens for clinical laboratory testing at Visit 1 (Screening) and, if possible, for Visit 6 (EOS). However, if a subject arrives at the clinic for Visit 6 (EOS) without having fasted for at least 8 hours, laboratory specimens may be collected as non-fasting, at the discretion of the Investigator and documented as such on the laboratory requisition form.

5.3.2 Activity

No activity restrictions are applicable.

5.4 Screen Failures

Screen failures are defined as subjects who consent to participate in the clinical study but are not subsequently randomized into the study. A minimal set of screen failure information is required to ensure transparent reporting of screen failure subjects to meet the Consolidated Standards of Reporting Trials (CONSORT) publishing requirements and to respond to queries from regulatory authorities. Minimal information includes demography, eligibility criteria, and any serious adverse event (SAE) will be collected and recorded in the electronic data capture system.

Individuals who do not meet the criteria for participation in this study (screen failure) may be rescreened.

Eligible subjects who are not able to complete all their screening assessments within the designated screening period may be rescreened at the discretion of the Sponsor. Rescreening for other reasons may be allowed after consultation with the Sponsor. All screening assessments except for the ICF/Assent, confirmation of CI diagnosis, height, and buccal swab for DNA will be repeated unless determined otherwise by the Sponsor.

Participants who have a clinically nonsignificant out-of-range laboratory result may be rescreened 1 time only at the discretion of the Investigator and after consultation with the Sponsor. For normal ranges, refer to the Laboratory Manual.

Rescreened subjects should not be assigned the same subject number as for the initial screening.

6.0 STUDY TREATMENT

6.1 Study Treatment(s) Administered

The blinded study treatments to be used in this study include:

- TMB-001, 0.05%, bid
- TMB-001, 0.1%, bid
- Vehicle Ointment (Control) bid

The study medication is intended to be applied twice daily, ideally once in the morning and once in the evening, but at least 6 hours apart.

Subjects are instructed to use the indicated amount of study medication on the VIIS Treatment/Assessment Areas. Refer to the Subject and Site Instruction Sheet for per protocol amounts of medication to be applied based on subject's BSA%.

Product application will be clearly demonstrated by the Investigator or a designated healthcare professional at the Baseline Visit.

The study treatment details are provided in [Table 2](#). The Vehicle ointment contains only the inactive ingredients and color additive so that the active and vehicle formulations are indistinguishable.

The Treatment/Assessment Areas are described in [Section 4.1.2](#).

Table 2 Study Treatments

Study Treatment Name:	TMB-001 0.05%	TMB-001 0.1%	Vehicle
Dosage Formulation:	Ointment	Ointment	Ointment
Unit Dose Strength(s)/Dosage Level(s):	0.05%	0.1%	Not applicable
Route of Administration	Topical	Topical	Topical
Dosing Instructions:	Twice daily (morning and evening)	Twice daily (morning and evening)	Twice daily (morning and evening)
Packaging and Labeling	Study medication will be provided in aluminum tubes. Each aluminum tube will be labeled as required per country requirement.	Study medication will be provided in aluminum tubes. Each aluminum tube will be labeled as required per country requirement.	Vehicle ointment will be provided in aluminum tubes. Each aluminum tube will be labeled as required per country requirement.
Manufacturer	Ferndale Laboratories in Ferndale, Michigan, USA	Ferndale Laboratories in Ferndale, Michigan, USA	Ferndale Laboratories in Ferndale, Michigan, USA

6.2 Preparation/Handling/Storage/Accountability

TMB-001 ointment and Vehicle ointment are manufactured in a current Good Manufacturing Practice (GMP)-compliant facility and tested prior to release to ensure that the quality characteristics of each clinical batch are met. TMB-001 ointment and Vehicle ointment are packaged in aluminum tubes and should be stored at the conditions specified on the label as follows:

- Store at 36°F to 46°F (2°C to 8°C) until dispensed. Once dispensed, store at 68°F to 77°F (20°C to 25°C), excursions permitted to 59°F to 86°F (15°C to 30°C).

For Subjects that will be seen in clinic for Visit 2, study medication will be shipped directly to the study site. The Investigator or designee must confirm that appropriate temperature conditions have been maintained during transit for all study medications received and any discrepancies are reported and resolved before use of the study medication.

For Subjects that will have Visit 2 performed remotely, the study medication will be shipped directly to the subject's home. The subject will receive confirmation from the courier that appropriate temperature conditions have been maintained during transit for all study medications received and the courier will report any discrepancies to the site. In case of discrepancies the site will ensure they are resolved before use of the study medication and communicate that to the subject.

Prior to using any tube, the tube must be weighed. Upon return of the tube to the study center, the tube must be weighed.

Only subjects enrolled in the study may receive study treatment, and only authorized study center staff may supply or administer study treatment. All study treatments must be stored in a secure, environmentally controlled, and monitored (manual or automated) area in accordance with the labeled storage conditions with access limited to the Investigator and authorized study center staff.

The Investigator or designee is responsible for study treatment accountability, reconciliation, and record maintenance (i.e., receipt, reconciliation, and final disposition records) using the Drug Accountability Form. These forms must be available for inspection at all times.

Further guidance and information for the final disposition of unused study medication are provided in the Investigator Study Binder.

6.3 Measures to Minimize Bias: Randomization and Blinding

Subjects who meet all inclusion criteria and no exclusion criteria will be randomized to a treatment group in a 1:1:1 ratio, stratified by CI subtype.

All subjects will be centrally assigned to randomized study treatment using an Interactive Web Response System (IWRS). Before the study is initiated, the log in information and directions for the IWRS will be provided to each study center.

Study medication use will be accounted and dispensed at the study visits as summarized in the Schedule of Activities ([Section 1.2](#)).

In this double-blind study, all personnel involved, ie, physicians, site staff, and participants will remain blinded at all times, except in an emergency, where knowledge of the randomization code is required to provide appropriate treatment. In case of an emergency, the Investigator has the sole responsibility for determining if unblinding of a subject's treatment assignment is warranted. Subject safety must always be the first consideration in making such a determination. If the Investigator decides that unblinding is warranted, every effort should be made to contact the Sponsor and Medical Monitor prior to unblinding a subject's treatment assignment unless this could delay emergency treatment of the subject. If a subject's treatment assignment is unblinded, the Sponsor must be notified within 24 hours after breaking the blind. The date and reason that the blind was broken must be recorded in the source documentation and electronic Case Report Form (eCRF), as applicable.

6.4 Study Treatment Compliance

The prescribed dosage, timing, and mode of administration may not be changed, except as defined in [Section 7.4](#). Any departures from the intended regimen must be recorded in the eCRFs.

During the course of the study, compliance to study drug application will be evaluated via Subject diaries and accountability by the site, including weighing the tubes. Subjects exhibiting poor compliance should be counseled on the importance of good compliance to the study dosing regimen.

6.5 Concomitant Therapy

Prohibited medications include the use of the following in the Treatment Areas:

- Topical retinoids or any other topical prescription or over-the-counter therapies that are intended for, or that in the opinion of the Investigator may improve, CI within 2 weeks of Visit 2 (Baseline) and until the Visit 6 (EOS);
- Keratolytics, or topical corticosteroids within 7 days prior to Visit 2 (Baseline) and until the Visit 6 (EOS); and,
- Topical products, at Visit 2 (Baseline) and until the Visit 6 (EOS). Bland emollients and over the counter low potency hydrocortisone (e.g., 1% cream) may only be used in the event of severe discomfort (e.g., burning/erythema/itch) and if it is the opinion of the Investigator that a drug interruption (per section 7.4) alone will not relieve the symptoms and these may

cause the subject to discontinue from study. The duration of the mitigation plan should not exceed 2 weeks.

- Topical antibiotic or antifungal can be used after consultation and at the discretion of the Investigator. Systemic antifungals or antibiotics must be prescribed by the Investigator if necessary to avoid risk of more serious or broader infections.

The following systemic treatments are prohibited:

- Vitamin A supplements or St. John's Wort within 4 weeks prior to Visit 2 (Baseline) and until the Visit 6 (EOS) Note: Use of a multivitamin including Vitamin A is not exclusionary provided it is taken as directed as on the packaging;
- Retinoids within 12 weeks of Visit 2 (Baseline) or any other systemic therapies which are intended for or may improve CI within 4 weeks of Visit 2 (Baseline) and until the Visit 6 (EOS); and,
- Immunosuppressive drugs, including systemic corticosteroids, within 2 weeks of Visit 2 (Baseline) and until the Visit 6 (EOS).

The use of UV light is prohibited within 4 weeks prior to Visit 2 (Baseline) and until the Visit 6 (EOS). Further, subjects should limit exposure to UV via sunlight and avoid tanning beds.

Subjects may not be enrolled in an investigational drug or device study or have used an investigational drug or investigational device treatment within 30 days prior to Visit 2 (Baseline).

Any medication or vaccine (including over-the-counter or prescription medicines, vitamins, and/or herbal supplements) that the subject is receiving at the time of enrollment or receives during the study must be recorded on the eCRF along with:

- Reason for use;
- Dates of administration including start and end dates; and,
- Dosage information including dose and frequency.

The Medical Monitor should be contacted if there are any questions regarding concomitant or prior therapy.

6.6 Dose Regimen Modification

Dose regimen modification is not allowed in this study, except for a structured treatment interruption scheme (drug holiday) as detailed in [Section 7.4](#).

6.7 Treatment after the End of the Study

The Sponsor will not provide any additional care to subjects after they leave the study because such care should not differ from what is normally expected for subjects with CI.

7.0 DISCONTINUATION OF STUDY TREATMENT AND SUBJECT DISCONTINUATION/WITHDRAWAL

See the Schedule of Activities ([Section 1.2](#)) for a list of the data to be collected at the time of treatment discontinuation and follow-up and for any further evaluations that need to be completed.

7.1 Pregnancy

Any female subject who becomes pregnant during the study must discontinue treatment. If a pregnancy is reported, the Investigator should inform the Sponsor within 24 hours of learning of the pregnancy and should follow the procedures outlined in [Section 8.4.5](#) and [Appendix 6](#).

7.2 Inadvertent Enrollment

If a subject who does not meet enrollment criteria is inadvertently enrolled, that subject must be discontinued from study treatment; and the Sponsor or Sponsor designee must be contacted.

7.3 Adverse Events

A subject may discontinue from the study due to an SAE or AE. In that case, the procedures in [Section 8.4](#) must be followed.

See the Schedule of Activities ([Section 1.2](#)) for data to be collected at the time of treatment discontinuation and follow-up and for any further evaluations that need to be completed.

7.4 Temporary Discontinuation (Drug Interruption/Holiday)

A treatment interruption scheme will be allowed if a subject experiences skin adverse events or LSRs during the study that may require interruption or termination of study medication. This is intended to assist subjects to continue in the study if the event is likely or expected to lead to discontinuation. Any subjects with a LSR (especially early during treatment) will be encouraged to continue with their study medication since transient skin irritation is known to develop with topical retinoids, but LSRs may also develop due to the vehicle formulation or other reasons.

It is desirable to make every effort to maintain subjects in the study to allow adequate assessment of efficacy and safety, especially in this small dose-ranging study. If during the Treatment Phase there is a persistent Grade 2 or greater adverse event, treatment can be temporarily interrupted, and unscheduled visits/phone calls will be scheduled to monitor resolution. Supportive action (per section 6.5) can be undertaken, if in the opinion of the Investigator the drug interruption alone will not relieve the symptoms and may cause the subject to discontinue from study. As soon as the LSR(s) have resolved, study medication will be restarted at a frequency of once daily for 2 weeks. If treatment is tolerated at this frequency, then treatment will be increased to twice daily or as per protocol. If necessary, a second drug interruption will be allowed according to the instructions above, as per the Investigator's discussion and agreement with the Medical Monitor.

Treatment will be permanently discontinued if any of the following occurs:

- If the LSR(s) do(es) not resolve with the interruption of therapy for 2 weeks, or
- If the LSR(s) recur(s) during bid dosing, or
- If a third drug interruption is needed.

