Each subject will participate in the study for up to 24 weeks (including up to a 90-day Screening period).

Eligible subjects will be randomized (1:1:1) to one of 3 treatment groups:

1. TMB-001, 0.05%, twice daily (bid)
2. TMB-001, 0.1%, bid
3. Vehicle Ointment (Control), 0%, bid

Temporary Discontinuation (Drug Interruption/Holiday)

A treatment interruption scheme will be allowed if a subject experiences skin adverse events or local skin reactions (LSRs) during the study that may require interruption or termination of study medication. This is intended to assist subjects to continue in the study if the event is likely or expected to lead to discontinuation. Any subjects with a local AE (especially early during treatment) will be encouraged to continue with their study medication since transient skin irritation is known to develop with topical retinoids, but AEs may also develop due to the vehicle formulation or otherwise.

It is desirable to make every effort to maintain subjects in the study to allow adequate assessment of efficacy and safety, especially in this small dose ranging study. If during the Treatment Phase there is for example a persistent Grade 2 or greater burning/stinging, erythema, erosions, edema or pruritus, treatment will be

temporarily interrupted (maximum of 2 weeks), and unscheduled visits/phone calls will be scheduled to monitor resolution. As soon as the LSR(s) have resolved, treatment will be restarted at a frequency of once daily for 2 weeks. If treatment is tolerated at this frequency, then treatment will be increased to twice daily or as per protocol. If necessary, a second drug interruption will be allowed according to the instructions above, as per the Investigator's discussion and agreement with the Medical Monitor. For details see section 6.5 and 7.4

Treatment will be permanently discontinued if any of the following occurs:

- If the LSR(s) do(es) not resolve with the interruption of therapy for 2 weeks, or
- If the LSR(s) recur(s) during bid dosing, or
- If a third drug interruption is needed.

Treatment/Assessment Areas:

Treatment/Assessment Areas are defined as:

Treatment area- the area of the entire body with active CI where the study medication will be applied (the entire body except for the hands, face, neck, scalp and genitalia are possible treatment areas.)

Assessment Area- For the purposes of assessing via the Visual Index for Ichthyosis Severity (VIIS)

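### If the same local skin reaction returns at persistent Grade 2 or worse after the return to twice-daily dosing, the protocol both allows a second interruption and requires permanent discontinuation, and does not say which prevails

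*Protocol*

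**What the plan says.** The scheme appears twice, in the synopsis (Protocol 1.1, under temporary discontinuation) and in Protocol 7.4.

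- **Trigger.** Section 7.4 refers to a "persistent Grade 2 or greater adverse event, treatment can be temporarily interrupted". It is set for the treatment phase as a whole and is not limited to one dosing frequency. The synopsis gives a list of reactions as examples, makes interruption the stated action and caps it at 2 weeks.
- **Restart.** Once the reaction has resolved, "study medication will be restarted at a frequency of once daily for 2 weeks".
- **Return to full frequency.** "If treatment is tolerated at this frequency, then treatment will be increased to twice daily or as per protocol".
- **Second interruption.** The next sentence in both places reads: "If necessary, a second drug interruption will be allowed according to the instructions above". The investigator must first discuss it with the Medical Monitor and obtain agreement.
- **Permanent stop.** "Treatment will be permanently discontinued if any of the following occurs". The list has three items: no resolution after 2 weeks off drug; "If the LSR(s) recur(s) during bid dosing, or"; and "If a third drug interruption is needed".

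The second-interruption sentence and the three stopping items match in the two places.

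**The concern.** The permission for a second interruption comes straight after the return to twice daily, and it borrows a trigger that is not confined to the once-daily period. The list below it then makes recurrence on twice-daily dosing a reason to stop for good. For one type of subject, the two sentences point in opposite directions.

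Which sentence is followed decides whether that subject stays on drug. It therefore affects exposure and the table of treatment-emergent adverse events leading to discontinuation of study treatment (Protocol 9.4.2). It could also affect the SAP's display of treatment success by interruption frequency, duration and outcome (SAP 9.2.3). The study has 15 subjects per arm and is meant to help choose a dose for Phase 3 (Protocol 9.2). Protocol 4.3 cites poorer tolerability at 0.2% as the reason for studying lower strengths, so tolerability bears on that choice.

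**Working it through.** The documents give no figure to reproduce. The check is whether the two rules can apply to the same subject, and whether that can happen within the study.

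**Step 1. Cases after a first interruption.**

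| Case | Second interruption available? | Recurrence item of the stopping list met? | Result |
|---|---|---|---|
| 1. Same LSR returns during the once-daily restart | Yes | No, dosing is not twice daily | No conflict |
| 2. A different LSR or other skin event appears on twice-daily dosing | Yes | No, if recurrence means the same reaction | No conflict on that meaning |
| 3. Same LSR returns on twice-daily dosing, persistent Grade 2 or worse | Yes, as the sentence is written | Yes | Both rules apply |
| 4. Same LSR returns on twice-daily dosing at a lower grade | No, trigger not met | Yes, the item names no grade | Stop required although the event would not justify an interruption |

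Only case 3 produces opposite actions. Case 4 shows a related gap: the recurrence item does not say what grade counts, or whether it refers to the first or the second interruption. Case 2 depends on a meaning of recurrence that is not stated.

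**Step 2. Can case 3 occur within 12 weeks?** Inputs are treatment of 12 weeks (Protocol 4.1), up to 2 weeks off drug (synopsis) and 2 weeks once daily (Protocol 7.4). Assume a first reaction at week 2.

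- Off drug until week 2 + 2 = 4.
- Once daily until week 4 + 2 = 6.
- Twice daily from week 6, leaving 12 − 6 = 6 weeks in which the reaction can return.

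In general, a first interruption that starts before week 12 − 4 = 8 leaves some twice-daily time even with the full 2 weeks off.

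**Step 3. What differs for one such subject (illustration).** Continue the example and assume recurrence at week 8, acted on at once. The full schedule is 12 × 7 × 2 = 168 applications. By week 8 the subject has applied 28 (2 weeks twice daily) + 0 + 14 (2 weeks once daily) + 28 (2 weeks twice daily) = 70.

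- Permanent stop: 70/168 = 41.7%, off drug from week 8 and counted as a treatment discontinuation.
- Second interruption, off to week 10 and then once daily to week 12: (70 + 14)/168 = 84/168 = 50.0%, on drug at Visit 6 and not counted as a discontinuation.

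Measured against the full twice-daily schedule, both are below the 80% needed for the per-protocol population. In this example the choice of rule changes the discontinuation count and treatment status at Week 12, but not per-protocol membership.

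**Step 4. Scale.** One subject is 1/15 = 6.7% of an arm. The documents give no recurrence rate, so the number of affected subjects cannot be estimated.

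**The case against.** The strongest reply is that the text has a natural order. The second interruption is conditional and permissive, while the list is mandatory and one item is enough. Permission followed by hard limits is ordinary drafting. On that reading case 3 has one outcome, and second and third interruptions remain possible through cases 1 and 2. A site also cannot grant a second interruption alone, because the Medical Monitor must agree.

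Much of this stands. A reader might infer that the two rules contradict each other outright, or that they fit only if the second interruption is confined to the once-daily period. The documents do not support either: a different skin event on twice-daily dosing could also justify a second interruption without meeting the recurrence item.

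A reader might also infer that sites are bound to act differently. That is possible but not established, and the Medical Monitor's role reduces the risk. It does not remove it, because a site that goes straight to the stopping list is not directed to consult anyone.

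Nor do missing Week 12 scores follow. Protocol 8.1.4 asks subjects discontinued from the study early to complete the end-of-study procedures at their last or early termination visit. Discontinuation is not a listed endpoint either. It is tabulated by arm, with no test planned.

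What remains is that the reconciling reading is the reader's own. No passage states the scope, the meaning of recurrence or the precedence. The stated aim of Section 7.4, to keep subjects in the study, could lead a reasonable site towards the second interruption.

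**Conclusion.** The point holds in a narrow form. In the synopsis and in Section 7.4, a subject whose same LSR returns at persistent Grade 2 or worse on twice-daily dosing meets two written rules with opposite actions. A consistent reading is available but not stated, so sites could act differently on a matter that affects subject management, exposure and the tabulated discontinuations.

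This rests on taking recurrence to mean the same reaction and on the interruption trigger applying at any dosing frequency, as written. The scale is 6.7% of an arm per affected subject, with the number affected unknown. No endpoint definition, sample size or error rate changes. It should be corrected because it concerns how subjects are managed and the correction is cheap.

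**What to change.** Reconcile the two rules in the synopsis and in Section 7.4 so that recurrence of the same LSR during twice-daily dosing leads to one stated action. The revised text should say:

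- which events, and which dosing period, the second interruption covers;
- what counts as recurrence, including the grade and whether it refers to the first or the second interruption;
- which rule prevails where both apply.

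The choice of action is a clinical decision for the sponsor, and none is proposed here.

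Add to the eCRF a field for the listed criterion that triggered each permanent stop. Interruptions are already to be listed (SAP Appendix 1) and regimen departures recorded (Protocol 6.4), so this field is the only new data item. The cost is amendment wording in two places and one eCRF field.
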